9.3.3. Potential Hy's Law Events

Participants with elevated ALT or AST $> 3 \times$ ULN range and alkaline phosphatase $< 2 \times$ ULN range accompanied by total bilirubin $> 2 \times$ ULN range at the same visit will be listed by treatment group.

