Study Schedule/Procedures: Subjects will undergo screening assessments, including physical examination; laboratory tests, including pregnancy and serology tests; an ECG; and a bone marrow examination to determine eligibility. During the treatment period, subjects will be monitored for safety through disease-specific physical examinations, including vital signs, ECOG performance status, assessment of AEs, ECGs, and laboratory assessments every 4 weeks through Week 48 and then every 12 weeks thereafter. Hematology will be assessed every 2 weeks for the first 8 weeks. Disease status will be assessed (using the same modality [CT/MRI] from screening) every 8 weeks through Week 24, then every 12 weeks through Week 96, and then every 24 weeks thereafter until disease progression.

[REDACTED]

Subjects withdrawn from study treatment for reasons other than disease progression will be followed for disease status until radiologic disease progression, the start of a new anticancer therapy, consent withdrawal, or death (whichever occurs first). After permanently discontinuing study treatment, subjects will be followed every 12 weeks for subsequent anticancer therapies and survival.

Estimated Duration of Participation: Subject participation from screening through follow-up is expected to average approximately 26 months, which includes the following:

- A screening period lasting up to 28 days.
- A treatment period lasting as long as the subject is receiving benefit, tolerating the regimen, and has not met withdrawal criteria (approximately 14 months).
- A safety follow-up period lasting 30 to 35 days.
- A disease and survival follow-up period until the end of the study.

At the end of the study, subjects who have completed at least 24 months of study participation (starting from first dose of INCB050465), who remain on active study treatment, and who have no evidence of progressive disease will have the option to continue on monotherapy with INCB050465 provided within a rollover Protocol, as local law permits.

Estimated Number of Subjects: Approximately 190 subjects were planned to be enrolled and allocated to either Cohort 1 (received prior ibrutinib; n = 60-90) or Cohort 2 (have not received prior BTK inhibitor; n = 60-100). Cohort 1 will be closed to further enrollment by Protocol Amendment 7 with approximately 50 subjects enrolled. The estimated total number of subjects to be enrolled in the study is approximately 150.

Principal Coordinating Investigator:

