5.4.1.1. Dose Modifications

Dose modification guidance for AEs that have been previously observed in subjects receiving INCB050465 or are potential class-effect AEs are provided (see [Table 3](#) and [Table 5](#)). The starting dose and dose reduction levels of INCB050465 are provided (see [Table 4](#)). Individual decisions regarding dose interruption and reduction should be made using clinical judgment and in consultation with the sponsor's medical monitor, taking into account relatedness of the AE to the study treatment and the subject's underlying condition. Adverse events that have a clear alternative explanation or transient (≤ 72 hours) abnormal laboratory values without associated clinically significant signs or symptoms may be exempt from dose reduction guidelines

Table 3: Guidelines for Interruption and Restarting INCB050465

ADVERSE EVENT	ACTION
Chemistry	

 Grade 3 AST and/or ALT ($> 5.0 \times \text{ULN}$). 
Note: In subjects with liver metastasis-related elevations at baseline, contact sponsor to discuss clinical management and possible dose reductions.
	
Step 1: Interrupt INCB050465 and monitor weekly until the toxicity has resolved to Grade ≤ 1.
 
Step 2: Restart INCB050465 at next lower dose with medical monitor approval. Monitor as clinically indicated.

Hematology	

 Grade 3 ANC ($< 1.0 \times 10^9/\text{L}$) Grade 2 platelet count (50 to $< 75 \times 10^9/\text{L}$) for subjects who enrolled with platelets $> 100 \times 10^9/\text{L}$. Grade 3 platelet count ($< 50 \times 10^9/\text{L}$) for subjects who enrolled with platelets $\leq 100 \times 10^9/\text{L}$. 	
Step 1: Interrupt INCB050465 up to 14 days until the toxicity has resolved to Grade ≤ 1 or pretherapy baseline. For Grade 3 ANC, monitor at least weekly.
 
Step 2: Restart INCB050465 at same dose; monitor as clinically indicated.

 Grade 4 ANC ($< 0.5 \times 10^9/\text{L}$). Grade 3 or Grade 4 febrile neutropenia. Platelet count is Grade 4 ($< 25 \times 10^9/\text{L}$). 	
Step 1: Interrupt INCB050465 up to 14 days until the toxicity has resolved Grade ≤ 2. (Monitor at least weekly.)
 
Step 2: Restart INCB050465 at same dose. Monitor as clinically indicated. If recurs, restart at next lower dose.

Other toxicities	

 Diarrhea/colitis. 	See Table 5 .

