- ^e Height required at screening only.
- ^f Timed triplicate ECGs will be obtained during the Day 1 visit (predose) and Week 4 visit (predose and 1.5 hours [\pm 15 minutes] after receiving study treatment).
- ^g Required at baseline except for reasons provided in Section 7.6.2.
- ^h If disease is present in bone marrow at baseline, a bone marrow biopsy will be required to confirm CR or may be performed as clinically indicated.
- ⁱ PJP prophylaxis should be given while subjects are receiving study treatment and continue for at least 2 to 6 months after the last dose of study treatment.
- ^j May be conducted by clinic visit, telephone, or email.

Table 7: Schedule of Laboratory Assessments

Laboratory Tests ^a	Section	Screening	Treatment				EOT	Safety Follow-Up
		Day -28 to -1	Day 1 ^b	Every 4 Weeks Through Week 48 (± 3 Days)	Every 12 Weeks From Week 48 (± 1 Week)	Other		EOT + 30-35 Days
Serum chemistries	7.5.7.1	X	X ^c	X	X		X	X
Hematology ^d	7.5.7.1	X ^e	X ^c	X	X	X ^f	X	X
Serology	7.5.7.3	X		X ^g	X ^g			
HIV testing	7.5.7.3.1	X ^h						
Serum pregnancy	7.5.7.2	X ⁱ					X	
Urine pregnancy	7.5.7.2					X ^j		
Tumor biopsy	7.8.5	X ^o				X ^p		

^a All laboratory assessments must be performed at a central laboratory, unless otherwise specified (see Section 7.5.7).

^b All laboratory assessments are to be performed before administration of study treatment on Day 1, unless otherwise specified.

^c If chemistry and/or hematology laboratory assessments occurred in the preceding 7 days, Day 1 assessments may be omitted.

^d Hematology samples will be collected every 2 weeks for the first 8 weeks.

^e Beta-2 microglobulin testing will be done at screening only.

^f Week 2 and Week 6 (± 3 days).

^g Samples for CMV DNA analysis only.

^h Optional for subjects enrolled in the United States.

ⁱ Only for females of childbearing potential; negative serum pregnancy test must be obtained within 14 days before administration of study treatment. Screening test may be performed centrally or at the investigative site laboratory.

^j Only for females of childbearing potential; if a urine pregnancy test is positive, then a serum pregnancy test should be performed. Urine pregnancy must be collected every 4 weeks until last dose of study treatment.

[REDACTED]

Table 8: Laboratory Tests: Required Analytes

Serum Chemistries	Hematology	Serology

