- Section 9.2.2 was updated to include details of analyses on time to onset of selected TEAEs of special interest. Summaries of longest duration of selected TEAEs of special interest were added to have a better understanding of the safety profile in terms of duration of class-effect AEs as well as AEs influenced by treatment regimens. "Grade 2 or higher" was changed to "Grade 3 or higher" for time to onset summary of rash. This change was made to be consistent with other PI3K inhibitors, which highlighted more severe cutaneous reactions graded as Grade 3 or higher in the labeling. "Herpes simplex virus infection" was changed to "herpes simplex" based on the MedDRA coding dictionary as a broader term. Exfoliative dermatitis was added to the list of TEAEs of special interest.
- Section 9.2.3 was updated to include summary of TEAEs by PT and maximum severity in decreasing order of frequency, summary of longest duration of selected TEAEs of special interest, and additional supporting summaries during the INCB050465 initial QD dosing period and the maintenance dosing period, which will provide supportive data of the safety profile of the maintenance dose. Summary of nonserious TEAEs by SOC and PT was removed because it will not be used for the clinical study report but will be provided for result disclosure.
- Section 9.3.2 was modified to include ALT and AST in the line graphs as additional supportive analyses for laboratory events of special interest.
- Section 9.3.3 was added to identify potential Hy's law events to better monitor liver toxicity.
- Section 9.3.4 was updated to align with the analysis plan for adverse events of special interest. Summary of worsening of laboratory events of special interest was removed because this is covered by the summary of worsening of laboratory abnormalities.
- Section 9.5 was updated to change the high threshold of QTcF and QTcB interval from 460 to 450 milliseconds for the purpose of analysis. This change is to comply with the categories outlined in FDA Guidance for Industry (E14 Clinical Evaluation of QT/QTc Interval Prolongation and Proarrhythmic Potential for Non-Antiarrhythmic Drugs) used to characterize outliers in QTc values.

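### The potential Hy's law listing requires all three liver criteria at one visit, so a participant whose bilirubin rises only after ALT/AST has fallen back can be left out

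*SAP*

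**What the plan says.** SAP 9.3.3 defines the listing. It begins "Participants with elevated ALT or AST" (above 3 × ULN), adds alkaline phosphatase below 2 × ULN and total bilirubin above 2 × ULN, and ends with the condition that these occur "at the same visit will be listed by treatment group". It gives no time window and does not say whether an unscheduled or local draw counts as a visit. SAP 11.2 gives the purpose: "Section 9.3.3 was added to identify potential Hy's law events to better monitor liver toxicity".

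Protocol Table 7 schedules serum chemistry "Every 4 Weeks Through Week 48 (± 3 Days"), then "Every 12 Weeks From Week 48", plus Day 1, end of treatment (EOT) and the safety follow-up visit at EOT + 30–35 days. The denser early sampling is for blood counts only: "Hematology samples will be collected every 2 weeks for the first 8 weeks".

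For Grade 3 ALT/AST (> 5 × ULN), Protocol Table 3 says "Interrupt INCB050465 and monitor weekly until the toxicity has resolved to Grade" 1 or lower. It does not say that the weekly sample includes bilirubin. Protocol 6.6 allows unscheduled visits, and Protocol 7.5.7 sends their samples to the central laboratory. Local values enter the eCRF only under the conditions stated there.

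**The concern.** The listing is the one planned output that is said to bring transaminases and bilirubin together for the same participant. If the two thresholds are crossed at different draws, the participant meets each part of the definition but never the whole. For example, ALT may be 10 × ULN at one draw and bilirubin 4 × ULN at a later one, by which time ALT is 3 × ULN or less.

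Such cases should be few. Protocol 1.3 reports no liver test abnormality above Grade 1 on treatment in 72 earlier subjects. The exact one-sided 95% upper bound is 1 − 0.05^(1/72) = 4.1%. With so few expected, one omission could change the listing from one case to none.

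**Working it through.** The SAP gives no figure to reproduce. The check has two parts.

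**Logic of the rule.** A later bilirubin rise is still listed if ALT/AST remains above 3 × ULN, with alkaline phosphatase below 2 × ULN, at that visit. It is lost only if ALT/AST has already fallen to 3 × ULN or below. With exponential decline, the half-life needed to stay above 3 × ULN until the next draw is gap × ln 2 / ln(peak/3):

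| Gap from ALT peak to next draw | Peak 5 × ULN | Peak 10 × ULN |
|---|---|---|
| 7 days | 9.5 days | 4.0 days |
| 28 days | 38.0 days | 16.1 days |
| 84 days | 114.0 days | 48.4 days |

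**What the rule costs.** All curve shapes here are assumptions; the documents give none. ALT rises linearly from 1 to 10 × ULN over 7 days, then declines with a half-life of 7 or 14 days. Bilirubin rises from 0.5 to 4 × ULN over 7 days, then declines with a half-life of 7 days. Lag means days from ALT peak to bilirubin peak. Alkaline phosphatase is taken to stay below 2 × ULN.

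- ALT crosses 3 × ULN at 7 × (3 − 1)/(10 − 1) = 1.56 days into its rise, which is day −5.44. It stays above until half-life × log2(10/3), which is day 12.16 (half-life 7) or day 24.32 (half-life 14).
- Bilirubin crosses 2 × ULN at 7 × (2 − 0.5)/(4 − 0.5) = 3 days into its rise and falls back to 2 × ULN 7 days after its peak. The window is lag − 4 to lag + 7, or 11 days.
- The chance of a same-visit listing is the overlap of the two windows divided by the draw interval, at most 1.

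| Draw interval | ALT half-life | Lag | Overlap (days) | Same visit | Any draws |
|---|---|---|---|---|---|
| 7 days | 7 | 7 | 12.16 − 3 = 9.16 | 100% | 100% |
| 7 days | 7 | 14 | 12.16 − 10 = 2.16 | 2.16/7 = 31% | 100% |
| 7 days | 7 | 28 | 0 | 0% | 100% |
| 7 days | 14 | 28 | 24.32 − 24 = 0.32 | 0.32/7 = 5% | 100% |
| 28 days | 7 | 0 | 11 | 11/28 = 39% | 39% |
| 28 days | 7 | 14 | 2.16 | 2.16/28 = 8% | 8% |
| 28 days | 7 | 28 | 0 | 0% | 11/28 = 39% |
| 28 days | 14 | 28 | 0.32 | 0.32/28 = 1% | 39% |
| 84 days | 7 | 0 | 11 | 11/84 = 13% | 13% |
| 84 days | 7 | 28 | 0 | 0% | 0% |

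A simulation with the draw schedule placed at random against the episode agrees (for example 0.305 for the second row and 0.399 for the any-draw figure in the seventh).

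Weekly draws give 100% in the last column because both windows are longer than 7 days. With wider spacing, using different draws helps only if one draw falls in the ALT window and the next in the bilirubin window. That needs a lag above interval − 5.44 − 7, which is 15.6 days for 28-day draws and 71.6 days for 84-day draws.

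One limit applies to the weekly rows. They assume that bilirubin is measured and that weekly draws continue until it rises. Table 3 requires weekly monitoring only until Grade 1 or lower, and after restart monitoring is as clinically indicated.

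**The case against.** **The schedule, not the rule, causes most losses at wide spacing.** This stands. A reader might take the 4- and 12-week intervals as the measure of the problem, dividing an assumed 7–14 days of joint elevation by the interval (7/28 = 25% to 14/28 = 50%; 7/84 = 8% to 14/84 = 17%). Those ratios say how often a scheduled draw lands in the overlap. They do not say how many cases the same-visit condition discards. An episode that was never sampled cannot be recovered by any listing rule.

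**The values appear elsewhere.** SAP Appendix A plans listings of all chemistry values (2.8.2) and abnormal ones (2.8.4). The shift tables use the worst postbaseline grade whatever the visit, and time to onset is planned for ALT and AST. So the case is lost from one listing, not from the data. But none of these outputs is stated to pair ALT/AST with bilirubin by participant, so a reader would have to find the case by hand.

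**Participants are protected by other means.** This also stands. A reader might infer a risk to participants. The listing is a planned output for the Clinical Study Report. Protection rests on Protocol Table 3, the ALT/AST events of special interest (8.5), 24-hour SAE reporting (8.3.2) and IDMC review, none of which depends on the listing.

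**A concurrent definition is a legitimate choice.** Nothing in the documents contradicts it, and a wider one admits unrelated peaks. That argues for keeping the same-visit cases identifiable, not for hiding the others.

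**Conclusion.** The gap holds as a possibility: a participant can be omitted when bilirubin exceeds 2 × ULN only after ALT/AST has fallen to 3 × ULN or below. The documents do not support the stronger reading that any bilirubin rise after the transaminase peak is missed, because it is listed while ALT/AST is still above 3 × ULN and alkaline phosphatase below 2 × ULN.

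Under the assumed curves, the rule costs most with weekly follow-up and a lag of two weeks or more, or with 4-week draws and a lag of about 4 weeks. It cost nothing with 4-week draws at lags of 0 to 14 days, or with 12-week draws at lags up to 28 days. These figures show where the rule matters; they do not estimate how many cases this trial would lose. The point is a cheap improvement to one safety-reporting output.

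**What to change.** In SAP 9.3.3 and Listing 2.8.5, include every participant with any postbaseline ALT or AST > 3 × ULN and any postbaseline total bilirubin > 2 × ULN. Use all scheduled, unscheduled and recorded local draws through the safety follow-up visit. Do not cut off at 30 days after the last dose: safety follow-up chemistry is scheduled at EOT + 30–35 days, so that limit would discard most of it.

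For each participant show:

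- the dates of the elevations and the days between the two peaks;
- alkaline phosphatase at those dates;
- baseline bilirubin;
- a flag for meeting all three criteria at one visit, so that the currently defined set is preserved.

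The cost is one reprogrammed listing from data already collected. The downside is some extra cases to review and rule out. Participants with Gilbert's syndrome or with liver metastases and raised ALT/AST can be eligible (inclusion criteria 9d and 9e). With treatment expected to last about 14 months, some peaks will be far apart and unrelated, and the dates and the interval let a medical reviewer see this. No dosing, monitoring or discontinuation rule changes.

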9.3.4. Worsening Laboratory Events of Special Interest

Laboratory events of special interest are listed below.

- ALT increased
- AST increased
- Absolute neutrophil count decreased

The time to onset of a worsening laboratory event is defined as the interval between the date of first dose of study drug and the date of the first occurrence of CTC grade worse than baseline for the laboratory event. Participants who have not experienced a worsening laboratory event at the time of analysis will be right-censored at the last postbaseline study visit with nonmissing CTC grade of the laboratory event.

Time to onset of worsening Grade 3 or 4 laboratory events of special interest will be summarized using descriptive statistics and the life-table method as described in Section 9.2.2, and the Kaplan-Meier plot of time to onset of worsening Grade 3 or 4 absolute neutrophil count decreased will be provided. Laboratory events of special interest to be summarized may be adjusted based on emerging data.

9.4. Vital Signs

Values at each scheduled visit, change, and percent change from baseline for vital signs, including systolic blood pressure, diastolic blood pressure, pulse, body temperature, respiratory rate, and weight will be summarized descriptively.

Normal ranges for vital sign values are defined in Table 4. The abnormal values for participants exhibiting vital sign abnormalities will be listed along with their assigned treatment regimen. Alert vital signs are defined as an absolute value outside the defined range and percentage change greater than 25%. Note that the definition of alert vital signs does not apply for body temperature and weight. The abnormal values for participants exhibiting alert vital sign abnormalities will be listed.

Table 4: Normal Ranges for Vital Sign Values

Parameter	High Threshold	Low Threshold
Systolic blood pressure	≤ 155 mmHg	≥ 85 mmHg
Diastolic blood pressure	≤ 100 mmHg	≥ 40 mmHg
Pulse	≤ 100 bpm	≥ 45 bpm
Temperature	≤ 38°C	≥ 35°C
Respiratory rate	≤ 24 breaths/min	≥ 12 breaths/min

9.5. Electrocardiograms

Twelve-lead ECGs including PR, QRS, QT, QTcB, QTcF, and RR intervals will be obtained for each participant during the study. Values at each scheduled visit, change, and percent change from baseline will be summarized for each ECG parameter. Baseline will be determined as the average of all nonmissing values before the first administration of INCB050465.

Normal ranges for ECG values are defined in Table 5. Electrocardiogram values will also be considered abnormal if the absolute percentage change from baseline is more than 25% (30% for QRS interval). Participants exhibiting ECG abnormalities will be listed with study visit and assigned treatment regimen. Abnormal values for participants with alert ECG values, defined as both the absolute value and the percentage change from baseline being outside normal ranges, will be identified and listed. Outliers of QT, QTcB, and QTcF values, defined as absolute values > 450 milliseconds or change from baseline > 30 milliseconds, will be summarized.

Table 5: Normal Ranges for Electrocardiogram Values

Parameter	High Threshold	Low Threshold
PR	≤ 220 ms	≥ 75 ms
QRS	≤ 120 ms	≥ 50 ms
QT	≤ 500 ms	≥ 300 ms
QTcB, QTcF	≤ 450 ms	≥ 295 ms
RR	≤ 1330 ms	≥ 600 ms

QTcB = Bazett's correction; QTcF = Fridericia's correction.

10. INTERIM ANALYSES

An interim futility analysis is planned for each of the cohorts when 30 participants have been treated and have been evaluated for response or have permanently discontinued study treatment because of disease progression, withdrawal of consent, or death.

Cohort 1 will be terminated for futility if ≤ 3 of the 30 participants responded (ie, CR or PR) based on assessments provided by the IRC; otherwise, the study for Cohort 1 will continue. The probability of stopping at interim for futility is 0.51 when the true response rate is 12%, 0.12 when the true response rate is 20%, or 0.02 when the true response rate is 28%.

Cohort 2 will be terminated for futility if ≤ 10 of the 30 participants responded (ie, CR or PR) based on assessments provided by the IRC; otherwise, the study for Cohort 2 will continue. The probability of stopping at interim for futility is 0.29 when the true response rate is 40%, 0.05 when the true response rate is 50%, or 0.003 when the true response rate is 60%.

An IDMC will be charged with evaluating interim futility results. The IDMC will consist of clinicians and an independent statistician. The IDMC will make recommendations to the sponsor at the planned interim futility analysis for both cohorts. The process by which the IDMC will make recommendations and decisions will be documented in the IDMC Charter. Additional operational details of the interim analyses, including tables, figures, and listings provided to the IDMC, will be provided in the IDMC Charter.

11. CHANGES AND MODIFICATIONS TO THE ANALYSIS PLAN

All versions of the SAP are listed in [Table 6](#).

Table 6: Statistical Analysis Plan Versions

SAP Version	Date
Original	04 FEB 2019
Amendment 1	27 AUG 2020
Amendment 2	28 JAN 2021

11.1. Changes to Protocol-Defined Analyses

The PP population was removed from the planned analysis. For a single arm, open-label study, the determination of participants to be excluded from the PP population is post hoc and may not be done objectively; thus, analysis based on this population may not be meaningful.

11.2. Changes to the Statistical Analysis Plan

Amendment 2 (28 JAN 2021)

Overall Rationale for the Amendment: The primary purpose of this amendment is to comply with responses to comments provided by FDA regarding the Statistical Analysis Plan Amendment 1.

- Section [6.4](#) was updated to include the summary for the number of dose reductions and the number of dose interruptions of each participant.
- Section [7.3](#) was updated to include the timing of primary efficacy analysis.
- Section [7.3.1](#) was updated to include a sensitivity analysis of ORR that summarizes participants who switched to the selected dose after starting the maintenance dose in a separate treatment regimen and to include an additional analysis on the number of participants who achieved best overall response after the time of crossover along with the best overall response data for this separate treatment regimen.
- Section [7.3.2](#) was revised to update the subgroup analysis by number of prior systemic therapy regimens at 1 vs 2-3, because historical clinical evidence suggests that third-line or later participants may have a poorer outcome compared with second-line participants in MCL.
- Section [7.4.1](#) and Section [7.4.3](#) were updated to included sensitivity analyses where response assessments after the time of crossover will be excluded from the determination of DOR and PFS for participants who switched to the selected treatment regimen after starting the maintenance dose.
- Section [7.4.2](#) was updated to include a sensitivity analysis of CRR by summarizing participants who switched to the selected dose after starting the maintenance dose in a separate treatment regimen.

- Section 9.2.1 was modified to clarify how AEs that occur after new anti-lymphoma therapy will be assessed.
- **Incorporation of minor changes.** Other minor changes have been incorporated throughout the SAP and are noted in the redline version of the amendment.

Amendment 1 (27 AUG 2020)

- Section 3 was revised to state that 40 additional participants will be added to Cohort 2 rather than 30 additional participants, thus increasing the total number of participants in Cohort 2 from 90 to 100. This change is to comply with recommendations from FDA to achieve a sufficient number of participants in Cohort 2 to support registration.
- Section 4.1.4 was updated to include details of rules for handling partial/missing onset or end date of TEAEs in the calculation of time to onset or duration of a TEAE. Rules for partial/missing date of last dose were updated to include details for when both month and day are missing.
- Section 5.2 was modified to provide details regarding how crossover participants will be summarized.
- Section 5.3 was updated to remove the efficacy evaluable analysis set and use the FAS for all analyses of efficacy data. This change is to comply with comments from FDA that any participants who received at least 1 dose should be included in the efficacy analyses for a single-arm trial. The all-screened population was added for the summary of analysis populations.
- Section 6.1.1 was modified to add geographic region to the summary of demographic and baseline characteristics because it is one of the subgroups used for analyses on ORR.
- Section 6.1.2 was modified to remove summaries of tumor markers but only keep listings. Relapsed/refractory status to the most recent prior therapy was added to the summary table of disease history because the response to last regimen before entering the study may be a prognostic factor for clinical outcomes.
- Section 6.2 was modified to add summaries of participants who are ongoing with treatment or still in the study.
- Section 6.4 was modified to change the calculations of duration of treatment and average dose during the maintenance dosing period because Group B with 2.5 mg QD was selected as the maintenance dose.
- Section 7.3.1 was modified to replace the efficacy evaluable analysis set with the full analysis set. This change is to align with Protocol Amendment 7 dated 30 JAN 2020 and include all treated participants in the efficacy analyses to comply with comments from FDA.
- Section 7.3.2 was modified to add "unknown" as a category for bone marrow involvement at baseline. Relapsed/refractory status to the most recent prior therapy was added to the subgroup analysis because the response to last regimen before entering the study may be a prognostic factor for clinical outcomes.

- Section 7.4.3 was modified to update references of censoring for PFS.
- Section 9.2.2 was updated to include details of analyses on time to onset of selected TEAEs of special interest. Summaries of longest duration of selected TEAEs of special interest were added to have a better understanding of the safety profile in terms of duration of class-effect AEs as well as AEs influenced by treatment regimens. "Grade 2 or higher" was changed to "Grade 3 or higher" for time to onset summary of rash. This change was made to be consistent with other PI3K inhibitors, which highlighted more severe cutaneous reactions graded as Grade 3 or higher in the labeling. "Herpes simplex virus infection" was changed to "herpes simplex" based on the MedDRA coding dictionary as a broader term. Exfoliative dermatitis was added to the list of TEAEs of special interest.
- Section 9.2.3 was updated to include summary of TEAEs by PT and maximum severity in decreasing order of frequency, summary of longest duration of selected TEAEs of special interest, and additional supporting summaries during the INCB050465 initial QD dosing period and the maintenance dosing period, which will provide supportive data of the safety profile of the maintenance dose. Summary of nonserious TEAEs by SOC and PT was removed because it will not be used for the clinical study report but will be provided for result disclosure.
- Section 9.3.2 was modified to include ALT and AST in the line graphs as additional supportive analyses for laboratory events of special interest.
- Section 9.3.3 was added to identify potential Hy's law events to better monitor liver toxicity.
- Section 9.3.4 was updated to align with the analysis plan for adverse events of special interest. Summary of worsening of laboratory events of special interest was removed because this is covered by the summary of worsening of laboratory abnormalities.
- Section 9.5 was updated to change the high threshold of QTcF and QTcB interval from 460 to 450 milliseconds for the purpose of analysis. This change is to comply with the categories outlined in FDA Guidance for Industry (E14 Clinical Evaluation of QT/QTc Interval Prolongation and Proarrhythmic Potential for Non-Antiarrhythmic Drugs) used to characterize outliers in QTc values.

